#### 5.7.2.1. Continuous Endpoints Anticipated to have a Normal Distribution

Continuous secondary variables defined in Section 4.7.2 and Section 4.7.3 anticipated to have a normal distribution (including HbA1c, fasting glucose, and liver fat) will be analyzed using a similar MMRM model as described for the primary endpoint in HbA1c.

Daily lipodystrophy hunger questionnaire (DLHQ) will be descriptively summarized from baseline to week 12 and again from baseline to week 24. Mean changes in monthly averaged DLHQ scores (±SE) will be plotted across visits by treatment group; a spaghetti plot will be provided for individual patient data across visits by treatment group. Monthly averaging windows of the DLHQ scores are defined in the Efficacy Analysis Windows for Daily Lipodystrophy Questionnaire (See Appendix 10.2). If a participant reported less than 10 scores

Protocol: R4461-PLD-20100

within a monthly averaging window for a DLHQ item, the averaged score will be assigned a missing value.

The statistical estimates, comparisons, and descriptive statistics for these secondary efficacy variables are summarized in Table 3, Table 4, Table 5, and Table 6.

Table 3. Summary of Statistical Estimates and Comparisons in Normally-distributed Secondary Endpoints

Endpoint	Cohort for Modeling	Analysis Method / Estimates	Comparisons
• Absolute change in HbA1c from baseline to week 12.	• Separately for Cohort B and Cohort A+B	MMRM / Least-squares (LS) means with their corresponding standard errors and 95% confidence intervals.  Note: Strata level = HbA1c>7.0%.  Note: Post baseline visits to include in the model are weeks 4, 6, 10, and 12.	REGN4461 versus Placebo with nominal p- value.
• Change in fasting glucose from baseline to week 12.	• Separately for Cohort A, Cohort B, and Cohort A+B	MMRM / Least-squares (LS) means with their corresponding standard errors and 95% confidence intervals.  Note: Strata level = HbA1c>7.0%.  Note: Post baseline visits to include in the model are weeks 2, 4, 6, 8, 10, 11, and 12.	REGN4461 versus Placebo with nominal p- value.
• Percent change in liver fat (MRI-PDFF) from baseline to week 12	• Separately for Cohort A, Cohort B, and Cohort A+B	MMRM / Least-squares (LS) means with their corresponding standard errors and 95% confidence intervals.  Note: patient subgroup = baseline MRI-PDFF ≥8.5%  Note: Post baseline visit at week 12.	REGN4461 versus Placebo with nominal p- value.

Protocol: R4461-PLD-20100

Table 4. Summary of Descriptive Statistics for Patients Randomized to REGN4461 in Normally-distributed Secondary Endpoints for the combined DBTP and SBTP Analysis

NOTE: These descriptive statistics will be presented three times, specifically in Cohort A, Cohort B, and Cohort A+B.

Endpoint		Descriptive Statistics
•	Absolute change in HbA1c from baseline to week 24	For Arm 2, descriptive summaries will be provided at each protocol specified visit up to week 24; mean changes (±SE) will be plotted across visits by treatment group; a spaghetti plot will be provided for individual patient data across visits by treatment group. These descriptive statistics will be provided twice, specifically for patients with baseline HbA1c>7% and again for All Patients.
•	Change in fasting glucose from baseline to week 24	For Arm 2, descriptive summaries will be provided at each protocol specified visit up to week 24; mean changes (±SE) will be plotted across visits by treatment group; a spaghetti plot will be provided for individual patient data across visits by treatment group. These descriptive statistics will be provided twice, specifically for patients with baseline HbA1c>7% and again for All Patients.
•	Percent change in liver fat (MRI-PDFF) from baseline to week 24	For patients with hepatic steatosis (baseline MRI-PDFF ≥8.5%) in Arm 2, descriptive summaries will be provided at each protocol specified visit up to week 24; mean changes (±SE) will be plotted across visits by treatment group; a spaghetti plot will be provided for individual patient data across visits by treatment group.

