3.2. Rationale

3.2.1. Rationale for Study Design

Rationale for Selection of Study Population:

This is a randomized, double-blind, placebo-controlled, study of the efficacy and safety of REGN4461 in patients with FPLD and metabolic abnormalities (elevated fasting TG with or without elevated HbA1c) who are not receiving recombinant human leptin (rhLeptin) therapy. The central hypothesis is that LEPR agonism will be effective in treating metabolic complications of leptin deficiency in PLD patients with low baseline leptin levels. This relationship between baseline leptin levels and REGN4461 response was borne out in the FIH R4461-HV-1794 Part B, where patients with leptin levels <5 ng/mL had the most robust response (weight loss), patients with leptin levels 5 ng/mL to 8 ng/mL had an intermediate response, and patients with leptin >8 ng/mL had no response.

The primary analyses of this study, therefore, include PLD patients with leptin levels <8.0 ng/mL (cohort A). A second cohort of PLD patients with leptin levels 8.0 ng/mL to ≤20.0 ng/mL (cohort B) will also be assessed (separately) given analyses of individualized patient data from the NIH which indicated patients with leptin level ≤20.0 ng/mL had a better response to metreleptin than did those with leptin level >20.0 ng/mL. Study eligibility and cohort allocation will be determined using an IUO leptin ELISA.

Partial lipodystrophy includes FPLD and APLD. The majority of patients that were studied in PLD metreleptin trials had FPLD. Acquired PLD patients comprise ~15% of PLD patients. Acquired PLD is thought to be caused by immune destruction of adipocytes. These patients can have one or more autoimmune diseases, eg, Type 1 diabetes, that might confound responses to leptin agonist therapy. For this reason, APLD patients are excluded from enrollment in this study.

Consensus diagnostic criteria for FPLD has been elusive (Brown, 2016). The phenotype of FPLD is similar to "metabolic syndrome" that affects 30% of individuals in the United States (US) (Moore, 2017). The main clinical distinction between common metabolic syndrome and FPLD is the selective loss of adipose tissue in FPLD patients, which can be a subtle and often overlooked physical exam finding. For this reason, regional lipoatrophy and metabolic complications, while not sufficient, are required inclusion criteria in this study.

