8.6. Method of Treatment Assignment

All patients will enter a 10-week screening period during which screening assessments will be performed, including fasting TG and leptin levels, to determine eligibility. All eligible patients will enter the 4-week single-blind placebo run-in period. Upon completion of the 4-week run-in period, up to 40 patients will be randomized in a 1:1 ratio to study arm 1 (placebo in TP1 and REGN4461 in TP2) or study arm 2 (REGN4461 in TP1 and TP2) according to a central randomization scheme provided by an interactive voice response system (IVRS)/interactive web response system (IWRS) to the designated study pharmacist (or qualified designee). Randomization will be stratified according to HbA1c levels (HbA1c ≤7.0% or HbA1c >7.0% at the screening visit) within each cohort.

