## **Sensitivity Analysis**

- A non-parametric approach will be performed on the primary efficacy endpoint for comparing the mibavademab and placebo. Specifically, the percent change in fasting serum TG from baseline to week 12 will be ranked for an analysis of covariance (ranked ANCOVA). For the case >5% missing data at week 12, missing data will be imputed using multiple imputation based on other observed measurements. The ranked ANCOVA model will be able to provide significance of the treatment effect as compared to placebo. Nominal p-values will be provided as a measure of the strength of evidence. Median treatment difference and its 95% confidence interval can be derived from the Hodges-Lehmann estimation and Moses distribution free confidence interval respectively.
- To assess the impact of a systemic dosing error on the primary efficacy endpoint, the primary efficacy analysis will be performed excluding affected patients. Patients known to be under dosed at the time of database lock will be identified for this analysis before database lock. Any additional patients determined to be affected post-database lock will be separately identified.

## 5.7.1.2. Change in HbA1c from Baseline to Week 12

Absolute change from baseline to week 12 in HbA1c, will be analyzed in the FAS population for the Cohort A patients using a mixed-effect model with repeated measures (MMRM) approach. The MMRM model will include the following effects: fixed categorical treatment groups (Placebo, mibavademab), time points (weeks 4, 6, 10, and 12), actual strata (screening HbA1c ≤7.0%, >7.0%), strata-by-time-point interaction, and treatment-group-by-time-point interaction, as well as the continuous fixed covariates of baseline HbA1c value and baseline value-by-time point interaction. An unstructured covariance matrix will be used to model the within patient errors. In the case that the unstructured covariance matrix does not converge, then a structured covariance matrix such as autoregressive heterogeneous [ARH] will be assessed.

Post-baseline data available up to and including the week 12 efficacy analysis window for HbA1c (Table 12 in Appendix 10.2) will be used and missing data are accounted for by the MMRM. Contrast and estimate statements will be used to assess baseline adjusted least-squares

Regeneron Pharmaceuticals, Inc.

Page 35 of 88

Protocol: R4461-PLD-20100

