#### 5.7.2.2. Continuous Endpoints Anticipated to have a Non-normal Distribution

Continuous secondary efficacy variables defined in Section 4.7.2 and Section 4.7.3 anticipated to have a non-normal distribution (ie, TG) will be analyzed using the same MMRM model as described for the primary endpoint in TG.

For comparisons that defined on the DBTP-stable Arm 1 patients, the MMRM model will be fitted again to exclude the Arm 1 patients who do not meet the DBTP-stability criteria. The LS means will be back-transformed into the geometric means to ease clinical interpretation of the result. Table 7 summarizes the statistical analysis methods that will be performed for the secondary efficacy variables in fasting TG.

Table 7. Summary of Statistical Estimates, Comparisons, and Descriptive Statistics in Fasting-TG Secondary Endpoints

Endpoints	Cohort		Estimates	Statistics
• Percent change in fasting TG from baseline to week 12.	fo B Co	eparately or Cohort and ohort +B	Baseline adjusted least-squares (LS) means estimates at week 12 for each treatment subgroup with their corresponding standard errors and 95% confidence intervals. The LS means at week 12 will be back-transformed into the geometric means.	Difference of the study treatment TG geometric mean changes from baseline to week 12 will be provided along with its corresponding 95% confidence interval, and nominal p-value.
• Percent change in fasting TG from baseline to week 24	fo A, B, Co	eparately or Cohort , Cohort , and ohort +B	N/A	For Arm 2 patients, descriptive summaries will be provided at each protocol specified visit up to week 24; median percent changes with Q1 and Q3 bars will be plotted across visits; a spaghetti plot will be provided for individual patient data across visits.

Protocol: R4461-PLD-20100

 
Percent change in fasting TG from baseline to week 12
 
Percent change in fasting TG from week 12 to week 24
 
	• Separately for Cohort A, Cohort B, and Cohort A+B	For Arm 1, baseline adjusted least-squares (LS) means estimates at week 12 and week 12 adjusted least-squares (LS) means estimates at week 24 will be provided with the corresponding standard errors and 95% confidence intervals. The LS means will be back-transformed into the geometric means.	For Arm 1, difference between the fasting TG geometric means from week 12 to week 24 and from baseline to week 12 will be provided along with its corresponding 95% confidence interval, and nominal p-value when appropriate.

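### The between-arm models for combined Cohorts A+B leave out leptin cohort, which is a randomisation stratum; the loss is small if the arms are balanced, and the term is cheap to add.

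*SAP*

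**What the plan says.** **Randomisation.** Patients are assigned to a leptin cohort and then randomised 1:1. Protocol 8.6 stratifies by screening HbA1c, "or HbA1c >7.0% at the screening visit) within each cohort". SAP 2.1 randomises each cohort separately, SAP 4.1 lists leptin among the IVRS randomisation strata, and SAP 5.1 names cohort as a stratification factor alongside HbA1c.

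**Primary models (Cohort A only).** The HbA1c MMRM in SAP 5.7.1.2 contains treatment, time point, "actual strata (screening HbA1c ≤7.0%, >7.0%), strata-by-time-point interaction, and treatment-group-by-time-point interaction", plus "the continuous fixed covariates of baseline HbA1c value and baseline value-by-time point interaction". The TG model in SAP 5.7.1.1 has the same structure. Neither contains cohort or leptin, and neither needs to in a single cohort.

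**Extension to A+B.** SAP 5.7.2.1 says HbA1c, fasting glucose and liver fat "will be analyzed using a similar MMRM model as described for the primary endpoint in HbA1c"; Table 3 applies this to HbA1c "Separately for Cohort B and Cohort A+B", and to glucose and liver fat in A, B and A+B. SAP 5.7.2.2 says TG "will be analyzed using the same MMRM model as described for the primary endpoint in TG", again including A+B (Table 7). No cohort term is introduced.

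**Expected cohort differences.** Protocol 3.2.1 reports that in the first-in-human study "patients with leptin >8 ng/mL had no response" (the outcome was weight loss). It also says that some data suggest response up to 20.0 ng/mL.

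**Whether the models will be run.** SAP 1.2.4 says that, because of early termination, efficacy output is limited to descriptive summaries and plots. SAP 5.7 still specifies the models.

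**The concern.** A factor that governs randomisation normally belongs in the model that analyses it. SAP 1.2.4 follows that principle for strata in general, replacing IVRS strata with actual strata in the models, but in the A+B fits only one of the two strata appears.

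Two things are at stake in the A+B between-arm contrasts. First, any difference in mean change between cohorts goes into the residual, so the interval is wider than it need be. Second, if the arms end up with different shares of Cohort A, part of that difference enters the treatment estimate. Randomisation within cohort limits this, but it does not guarantee balance in the liver-fat subset (baseline MRI-PDFF at least 8.5%, measured only at capable sites) or in a study stopped early with few patients.

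**Working it through.** **Inputs from the documents**
- Planned size: 20 per cohort, 10 per arm per cohort (Protocol 6.1.1), so 20 per arm in A+B.
- SD 1.81 for HbA1c change and 0.87 for log TG (Protocol 11.2).
- Placebo-adjusted effects −0.98 HbA1c points and −47% TG (Protocol Table 3 footnote). On the log scale, ln(0.53) = −0.635.

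**Assumptions (not in the documents)**
- No effect in Cohort B, the extreme reading of the first-in-human result.
- Cohort differences of 0.5, 0.75 and 1.0 SD.
- A 60/40 split of Cohort A between arms.

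**Reproducing the plan's figures.** Half-width = t(0.95, 2n−2) × SD × √(2/n) gives 1.724, 1.594 and 1.404 for HbA1c at 7, 8 and 10 per arm (stated 1.72, 1.59, 1.4), and 0.675 for log TG (stated 0.67). The inputs are therefore read correctly. The plan states no A+B figure.

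**Balanced arms: bias.** With effect −0.98 in A and 0 in B, the A+B estimate is −0.49 with or without a cohort term. There is no bias.

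**Balanced arms: precision.** If mean change, averaged over arms, differs between cohorts by d SDs, omitting cohort multiplies the SE by √(1 + d²/4).

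| Scenario | d | SE multiplier |
|---|---|---|
| HbA1c, full effect in A, none in B, no placebo difference: 0.98/2 = 0.49; 0.49/1.81 | 0.27 | 1.009 |
| TG, same scenario: 0.635/2 = 0.317; 0.317/0.87 | 0.36 | 1.016 to 1.017 |
| Assumed | 0.5 | 1.031 |
| Assumed | 0.75 | 1.068 |
| Assumed | 1.0 | 1.118 |

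At these effects, reaching d = 0.5 for HbA1c requires a placebo difference between cohorts of 0.905 − 0.49 = 0.415 points; d = 1.0 requires 1.81 − 0.49 = 1.32 points.

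**Coverage.** A simulation of 20,000 trials (one time point, 10 per arm per cohort, effect −0.98 in A and 0 in B) gave these results for nominal 95% intervals:
- No placebo difference: mean half-width 1.17 without cohort and 1.16 with it; coverage 95.5% in both.
- Cohort B higher by 0.98 points on placebo: coverage 97.0% without cohort and 95.2% with it; half-widths 1.26 and 1.16.

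The error is on the conservative side.

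**Unbalanced arms.** If Cohort A is 60% of one arm and 40% of the other, the shift is 0.2 × the cohort difference in mean change.
- Plan's effects: 0.2 × 0.49 = 0.098 HbA1c points; 0.2 × 0.317 = 0.063 log TG, or 6.6%.
- 0.5 SD: 0.2 × 0.905 = 0.18 points; 0.2 × 0.435 = 0.087 log, or 9%.
- 1.0 SD: 0.2 × 1.81 = 0.36 points; 0.2 × 0.87 = 0.174 log, or 19%.

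**Cost of the term.** At 20 per arm, one degree of freedom moves the 95% half-width for HbA1c from 1.159 to 1.160; at 16 per arm (78% with elevated HbA1c, rounded up), from 1.307 to 1.309.

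**What a cohort main effect does not do.** With no effect in B, the pooled effect is −0.25, −0.49 or −0.74 when A makes up 25%, 50% or 75% of patients. Adding cohort does not say which mixture is wanted; stated weights or a treatment-by-cohort term would.

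**The case against.** Several objections have force.

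- **The models may not be run.** On the text of SAP 1.2.4 only summaries and plots will be produced. This makes the model change conditional. It does not dispose of the point, because SAP 5.7 still specifies the models, and a crude pooled A+B difference is equally exposed to unequal cohort mix.
- **The evidence concerns response to drug, not change on placebo.** This stands. Taken alone it supports only about 1% to 2% SE inflation; larger figures need a placebo difference that no passage reports. Baseline value and HbA1c stratum are already in the model and may absorb part of any such difference.
- **Design limits imbalance.** Allocation is 1:1 within cohort, so the 60/40 split is an illustration, not an expectation.
- **The wording leaves room.** SAP 5.7.2.1 says only that the model is similar, which would permit a cohort term. SAP 5.7.2.2 says the TG model is the same, which would not.
- **Cohorts are also analysed separately**, so a difference in response would be visible anyway.

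A reader might infer that leptin cohort is, by the protocol's own hypothesis, the main predictor of response. The documents do not go that far. Protocol 3.1 expects improvement below 8.0 ng/mL without a comparison with Cohort B, Protocol 3.2.1 is hedged, and the Protocol Introduction cites metreleptin studies suggesting that patients with higher leptin also respond.

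A reader might also extend the imbalance argument to Table 6 and to the Arm 1 row of Table 7. Those are within-arm comparisons, so a cohort imbalance between arms cannot enter them.

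**Conclusion.** The point holds for the between-arm A+B contrasts: Table 3 and the baseline-to-week-12 row of Table 7. A declared randomisation stratum is missing from the specified models.

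The consequence is modest. With balanced arms there is no bias, and the SE is about 1% (HbA1c) to 2% (TG) too large on the plan's own effects, assuming none in Cohort B and no placebo difference. Inflation of 3% to 12% requires an assumed cohort difference of 0.5 to 1.0 SD. A shift in the estimate arises only if cohorts are unevenly split between arms: about 0.10 points or 6.6% for a 60/40 split on the plan's effects, and at most 0.36 points or 19% across the differences examined. It would be wrong to conclude that the planned A+B estimate is biased as it stands. These are secondary, nominal analyses in a study without formal testing. The change is worth making because it costs little and matches the analysis to the randomisation.

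**What to change.** 1. In SAP 5.7.2.1 and 5.7.2.2, state that the between-arm A+B models include cohort (A or B) as a fixed effect, and cohort-by-time-point where estimable.
2. Reconcile SAP 1.2.4 with SAP 5.7 so that it is clear whether these models will be fitted.
3. If only summaries are reported, present any A+B between-arm difference as a cohort-stratified average and state the weights. If the models are run, either state how cohort-specific effects are weighted or report the treatment-by-cohort estimate beside the pooled one.

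The cost is SAP wording and one degree of freedom for the main effect. With the interaction, the cohort terms come to as many as one parameter per visit: four for HbA1c and seven for TG and glucose. Liver fat has a single post-baseline visit and needs only the main effect. With few patients enrolled the interaction may not be estimable, so the SAP should allow falling back to the main effect alone. The Arm 1-only comparisons need no change on the ground of between-arm imbalance.

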# Table 5. Summary of Descriptive Statistics in Normally Distributed Secondary Endpoints based on REGN4461 Exposure

NOTE: Efficacy data for study treatment arm 1 (placebo) and arm 2 (REGN4461) will be combined by re-aligning to the first REGN4461 treatment administration, specifically study day 1 for arm 2 and week 12 for arm 1 will become REGN4461 Day 1. These descriptive statistics will be presented three times, specifically in Cohort A, Cohort B, and Cohort A+B.

Endpoints	Descriptive Statistic	
Absolute change in HbA1c from baseline to week 12	HbA1c mean changes from REGN4461     Day 1 to REGN4461 week 12 for combined DBTP-stable Arm 1 patients and Arm 2 patients will be provided along	

Regeneron Pharmaceuticals, Inc.

Page 38 of 88

Protocol: R4461-PLD-20100

• Absolute change in HbA1c from week 12 to week 24	with its corresponding 95% confidence interval.

 
Change in fasting glucose from baseline to week 12
 
Change in fasting glucose from week 12 to week 24
 
	• Fasting glucose mean changes from REGN4461 Day 1 to REGN4461 week 12 for combined Arm 1 and Arm 2 patients will be provided along with its corresponding 95% confidence interval.

 
Percent change in liver fat (MRI-PDFF) from baseline to week 12
 
Percent change in liver fat (MRI-PDFF) from week 12 to week 24
 
	• Liver fat (MRI-PDFF) mean changes from REGN4461 Day 1 to REGN4461 week 12 for combined Arm 1 and Arm 2 in patients with hepatic steatosis (baseline MRI-PDFF ≥8.5%) will be provided along with its corresponding 95% confidence interval.

Table 6. Summary of Statistics for Patients Randomized to Placebo in Normally distributed Secondary Endpoints

NOTE: These statistical estimates and descriptive statistics will be presented three times, specifically in Cohort A, Cohort B, and Cohort A+B.

Endpoints	Estimates	Comparison

 
Absolute change in HbA1c from baseline to week 12
 
Absolute change in HbA1c from week 12 to week 24
 
	
 
For Arm 1, baseline adjusted least-squares (LS) mean estimate at week 12 and week 12 adjusted least-squares (LS) mean estimate at week 24 will be provided along with the corresponding standard errors and 95% confidence intervals.
 
MMRM / Least-squares (LS) means with their corresponding standard errors and 95% confidence intervals.
 
Note: Treatment Group = Arm 1; Strata level = HbA1c>7.0%.
 
Note: Post baseline visits to include in the model are
 
	
 
For Arm 1, difference between the HbA1c mean changes from week 12 to week 24 and from baseline to week 12 will be provided along with its corresponding 95% confidence interval, and nominal p-value when appropriate.
 
REGN4461 in Arm 1 SBTP
 

Protocol: R4461-PLD-20100

	weeks 4, 6, 10, 12, 16, 18, 22, and 24.	versus Placebo Arm 1 DBTP

 
Change in fasting glucose from baseline to week 12
 
Change in fasting glucose from week 12 to week 24
 
	• For Arm 1, baseline adjusted least-squares (LS) means estimates at week 12 and week 12 adjusted least-squares (LS) means estimates at week 24 will be provided along with the corresponding standard errors and 95% confidence intervals.	• Within Arm 1 patients, difference between the fasting glucose mean changes from week 12 to week 24 and from baseline to week 12 will be provided along with its corresponding 95% confidence interval, and nominal p-value.

 
Percent change in liver fat (MRI-PDFF) from baseline to week 12
 
Percent change in liver fat (MRI-PDFF) from week 12 to week 24
 
	• For Arm 1 patients with hepatic steatosis (baseline MRI-PDFF ≥8.5%), baseline adjusted least-squares (LS) means estimates at week 12 and week 12 adjusted least-squares (LS) means estimates at week 24 will be provided along with their corresponding standard errors and 95% confidence intervals.	• Difference between the liver fat percent mean changes from week 12 to week 24 and from baseline to week 12 will be provided along with its corresponding 95% confidence interval, and nominal p-value.

